## 5. Objectives

---

### 5.1 *MAIN OBJECTIVE:*

**To evaluate the effectiveness of preservative-free ophthalmic formulation PRO-087 (by Laboratorios Sophia, S.A. de C.V.) to restore the anatomical and physiological characteristics of the ocular surface, as well as its distribution and the characteristics of the mild to moderate tear film dysfunction syndrome compared to Systane® Ultra and Ultra Systane® preservative free (by Laboratorios Alcon, S.A. de C.V.).**

### 5.2 *SPECIFIC OBJECTIVES:*

**5.2.1** To evaluate the safety of the preservative-free ophthalmic formulation PRO-087 (by Laboratorios Sophia, S.A. de C.V.) on the corneal and conjunctival epithelium, intraocular pressure, and structures of anterior and posterior segment in patients with tear film dysfunction syndrome from mild to moderate.

**5.2.2** To determine the correlation between improvement of clinical status and perceived improvement of symptoms of each participant in each study group.

**5.2.3** To compare the qualitative and quantitative histological status of the ocular surface before and after the pharmacological intervention in each study group to determine the evolution under the intervention of PRO-087.

**5.2.4** To evaluate the quantitative rating of tear film production by the Schirmer Test throughout the study.

**5.2.5** To qualitatively assess the tear film production by measuring the tear film break-up time stained with fluorescein and cobalt filter.

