Prevalence of the TDS, or Dry Eye Disease, is estimated from 15 to 34% on people over 65 years; this is an important data for it can mean bias on studies related with this ailment and its etiology, but mostly, it represents a group of people whose symptoms, related with the TDS, will remain with the long-term use of lubricants with preservatives.

Signs and symptoms of TDS, mainly conjunctival hyperemia, tearing, photophobia, burning and sense of a foreign body, are greater on patients using ophthalmic drugs with preservatives. This has been shown on multicenter studies, with significant results, where a prevalence of the signs and symptoms of a 30 to 50% was found.

It is possible to evaluate the clinical impact of these symptoms by different methods. The Schirmer Test reported a reduction of the tear production on 61% of the patients. The TBUT decreased on 78% of patients, fluorescein or lissamine green ocular surface staining show deficiencies on up to 22% of subjects.

Similarly, the impact on the daily life is significant. On a report, where the adherence to the treatment of patients using 1 or more ophthalmic drops with preservative was evaluated, it was found that 65% of the subjects has adverse events related to BAK, with hyperemia and sense of a foreign body as the first symptoms on 48% of the subjects.

Everything was related with the fact that at least 48% of the patients suspend the treatment due to ocular discomfort.

The long-term importance of toxicity caused by preservatives is evidenced with conjunctive and underlying tissues ultrastructural changes, i.e. increase of the amount of fibroblast on the own subepithelial substance, fibrosis and pseudopenfigoide reactions. Such changes have been related with the post-surgical tissue behavior in different procedures of patients with chronic diseases who used ophthalmic solutions with BAK for long periods, where satisfactory recovery, in terms of inflammation and wound healing, is not always as expected.

The most important short-term cell and structural changes are depletion of population of goblet cells, which are reduced on the ocular surface 50% after just 1 month of instillation of ophthalmic solutions with preservative. Likewise, instillation of 1 week on healthy patients has already a reduction on TBUT. The 6 months follow-up showed that 60% of subjects had a reduced TBUT, besides an alteration on the lipid layer.

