#### 10.4 Conjunctival Impression Cytology

Impression cytology of the bulbar conjunctiva is a procedure in which the quantity and quality of epithelial cells and component of the ocular surface are evaluated; the primary focus is to evaluate the density and amount of goblet cells in the sample. The observation will take place in the single and specialized center of pathology under digital counting and it will be confirmed by observation.

The procedure consists of the following steps:

1. Tetracaine instillation over the ocular surface
2. Eye speculum placing
3. A minicell will be taken with the mounted Millipore paper.
4. This will be placed manually in contact with the Millipore surface over the nasal bulbar conjunctiva, slightly pressing, without indenting the surface.
5. Cytological fixation spray will be applied (96% alcohol cytospray)
6. This will be placed on a clean and dry bottle to transport it to the sample gathering unit

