### 12.3 *Forbidden medications:*

Drug product group	Prototype	Route of administration	Washout period
Non steroid anti-inflammatory drugs	Ketorolac Bromfenac Diclofenac	Topical	2 weeks
Steroid anti-inflammatory drugs	Dexamethasone Prednisolone Fluorometholone	Topical and systemic	3 weeks
Prostaglandin analogues	Latanoprost Travaprost	Topical	4 weeks
Immunomodulators	Cyclosporine	Topical and systemic	2 months
Vasoconstrictors	Nafazoline	Topical	2 weeks
Agonists alpha 2	Brimonidine	Topical	3 weeks
Betablockers	Timolol, betaxolol	Topical	2 weeks
Preservative lubricants	Hirpomelose Sodium hyaluronate Propinylglycol	Topical	2 weeks

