5. OSDI
6. Goblet cells population

It is considered that the drug in evaluation PRO-087 is effective for use in patients diagnosed with mild to moderate tear film dysfunction, if they exhibit the changes marked in parameters (14.1.2) by more than 5% of subjects in both eyes, in compliance with all visits and adherence to treatment at an 80% during the time of study assessment.

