#### 14.1.2 Efficacy Assessment Parameters

Parameters	Value
Best-corrected visual acuity	Increase of 1 line in the Snellen chart or 1 logarithmic point (logMAR)
Corneal depithelization	Percentage of the damaged epithelium of the ocular surface, reduction of staining according to the oxford scale.
Tear film break-up time	Increase in the residence of the teal film, measured in seconds. Increase of 30% from baseline or equal or more than 10 sec.
Schirmer test	Increase of more than 30%
Adverse events	Presence of adverse events modifying some of the abovementioned criteria or others, evaluated as serious.
OSDI	Reduction of 20% of the total score from the baseline score.
Goblet cells population	Increase of 20% from baseline

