## 15. Proposed statistical analysis.

---

The statistical analysis will be performed by an investigator blinded to the intervention groups.

The continuous quantitative variables will be presented by measures of central tendency and dispersion (mean, standard deviation and ranges). Nominal and ordinal qualitative variables will be introduced by means of frequencies and ratios.

The Kolmogorov-Smirnov test will be performed to know the normal or abnormal distribution of the results obtained in each study group.

Assuming there is a normal distribution of data, the intra-group differences will be determined by an ANOVA test for repeated measures, with the Pearson correlation coefficient, for the quantitative variables.

For qualitative variables the  $\chi^2$  (chi square) test will be used and in case the expected frequencies are less than 5 the Fisher's exact test will be used.

The differences between groups will be analyzed using the ANOVA test for variance analysis, with the Pearson correlation coefficient, for the qualitative variables.

For qualitative variables, contingency tables 2x2 will be used and the differences will be calculated with  $\chi^2$  (chi square) with Yates's correction and in case the expected frequencies are less than 5 the Fisher's exact test will be used.

The significance level will be of a 0.05 alpha value or less.

The final statistical analysis will include all the subjects that complete the visits listed in the activity chronogram.

Also, those who have been assigned with a treatment (intervention) and attend at least to 1 visit after the baseline will be included and analyzed until the moment they attended.

Those who do not attend at least 1 follow up visit will be excluded.

Those who do not complete the visits will be classified as population with intention to treat.

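### Objective 5.2.3 answers the histology question for PRO-087 with a before/after contrast inside each arm, and section 15 does not say that the randomised between-arm difference decides it

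*Combined protocol and SAP*

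**What the plan says.** The main objective (5.1) is comparative: it concerns restoring the ocular surface and "the characteristics of the mild to moderate tear film dysfunction syndrome compared to Systane" Ultra, with and without preservative. Specific objective 5.2.3 is framed differently. It looks at qualitative and quantitative histology "before and after the pharmacological intervention in each study group to determine the evolution under the intervention of PRO-087", and asks for no contrast with either comparator.

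The histology comes from conjunctival impression cytology (10.4), where "the primary focus is to evaluate the density and amount of goblet cells in the sample". The schedule in section 9 places it at the baseline visit and at day 90 only.

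Section 15 says that, for quantitative variables and given normality, "the intra-group differences will be determined by an ANOVA test for repeated measures". It also plans an ANOVA for differences between groups, but that sentence assigns the test to the qualitative variables. One significance level, 0.05, covers everything. No test is linked to an objective and neither contrast is given precedence.

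The goblet-cell criterion in 14.1.2 is "Increase of 20% from baseline". Section 14.1 calls PRO-087 effective "if they exhibit the changes marked in parameters (14.1.2) by more than 5% of subjects in both eyes", subject to attendance and adherence conditions. No comparator enters that rule.

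**The concern.** A before/after change in one arm mixes whatever the product does with whatever happens to everyone in the trial: stopping a previous product, regular use of any lubricant, regression to the mean after selection on clinical thresholds, or drift in sampling and counting. Randomisation removes these from the difference between arms. It does not remove them from the change within an arm.

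The two contrasts can disagree on the same cytology data. If all arms improved alike, 5.2.3 as worded would report an improvement under PRO-087, while the between-arm comparison would show nothing to choose between the products. Because section 15 plans both tests and ties neither to 5.2.3, the choice could be made after the results are known. Goblet cells are also a listed efficacy variable in 14.1, so the answer bears on what may be claimed for the product.

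**Working it through.** **The plan's own figures.** There is no sample size, SD or expected change for goblet cells, so there is nothing to reproduce for this outcome. The number per arm comes from the Schirmer calculation in 13.3: 80 evaluable, 80 × 1.2 = 96 enrolled, 96 × 3 = 288. The 80 does not follow from its stated inputs: 2 × [(1.96 + 0.84) × 1.72 / 0.13]² ≈ 2,745 per group. That is a separate matter. The 80 is used here only as the planned evaluable number.

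**Which test answers 5.2.3.** Taken literally, section 15 gives quantitative variables the intra-group repeated-measures ANOVA and gives the between-group ANOVA to qualitative variables. A cell count is quantitative, so the literal text leaves it with the within-arm test alone. With two time points, repeated-measures ANOVA in one arm is the paired t-test (F = t²).

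**What each contrast estimates.** Let s be a change shared by all arms and e the part specific to a product.
- Within the PRO-087 arm: mean change = s + e(PRO-087).
- Between arms: [s + e(PRO-087)] − [s + e(comparator)] = e(PRO-087) − e(comparator).

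The shared part s cancels only in the second.

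**Illustration.** Assumptions: one normal change score per subject, 80 per arm, no difference between arms, two-sided 0.05 (section 13 uses 1.96; section 15 does not state sidedness), and a shared improvement of 0.1 to 0.5 SD of the change score. The range is assumed. The probability that the paired test shows a significant improvement under PRO-087 comes from the noncentral t with 79 degrees of freedom and noncentrality (shared change in SD) × √80, where √80 = 8.94.

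| Shared change (SD) | Noncentrality | Within-arm test significant, n = 80 | n = 96 |
|---|---|---|---|
| 0.1 | 0.89 | 14% | 16% |
| 0.2 | 1.79 | 42% | 49% |
| 0.3 | 2.68 | 76% | 83% |
| 0.4 | 3.58 | 94% | 97% |
| 0.5 | 4.47 | 99% | 99.8% |

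With no shared change, the within-arm rate of a false improvement is the nominal 2.5%. The between-arm ANOVA of change, simulated with 20,000 trials at 80 per arm, rejected in 5.2%, 4.9% and 4.9% of trials at shared changes of 0, 0.3 and 0.5 SD.

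**Precision given up.** The standard error of a within-arm mean change is SD/√80 = 0.112 SD. For a difference between two arms it is SD × √(2/80) = 0.158 SD, which is √2 = 1.41 times larger. The 95% half-widths are about 1.96 × 0.112 = 0.22 SD and 1.96 × 0.158 = 0.31 SD. A pairwise between-arm contrast has 80% power for about (1.96 + 0.84) × 0.158 = 0.44 SD, or about 0.49 SD with Bonferroni for two comparators.

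**The rule in 14.1.** Five per cent of 80 is 4, so five responding subjects in the PRO-087 arm exceed the limit, whatever the comparators show. This rule is also single-arm, and would contradict a reworded 5.2.3 if left as it is.

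**The case against.** The best reply is that the between-arm comparison is already there. The main objective is comparative and covers ocular-surface anatomy, goblet cells are an efficacy variable, and section 15 plans a between-group ANOVA. The reference to qualitative variables looks like a slip, since the next sentence deals with qualitative variables separately. This largely stands: the plan is not wholly within-arm, and a reader who infers that histology would be tested only by an uncontrolled contrast goes further than the text. What remains is that nothing says the between-arm test answers 5.2.3.

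Second, the objective speaks of evolution, not of effect or superiority, and names no test. A descriptive reading is legitimate, but the plan does not label it descriptive. A reader might also infer that a significant result in the PRO-087 arm will be set against a non-significant one in a comparator arm as proof of a difference. No section says that within-arm p-values will be compared across arms.

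Third, a reader might infer that equal recovery in all arms is likely, because section 3 says of goblet cells "which are reduced on the ocular surface 50% after just 1 month of instillation of ophthalmic solutions with preservative" and 12.3 lists "Preservative lubricants" with a two-week washout. The documents do not support this. Preserved artificial tears are among the interfering treatments excluded by 12.2.1. No goblet-cell recovery time and no share of former users is given. Systane Ultra is itself preserved (8.2), so on the background text the arms could diverge.

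Fourth, the percentages are a power curve: if a shared change is real, the paired test is right to detect it. This is correct. The error would lie in attributing that change to PRO-087, and the figures show only how often the occasion for it would arise under the assumed change.

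**Conclusion.** The point holds in a limited form. Objective 5.2.3 names an uncontrolled contrast where a randomised one is available from the same two cytology samples, and section 15 does not settle which one decides. The logic needs no numerical assumption: any shared change is included in a within-arm result and cancels between arms. The 14% to 99% against about 5% is illustrative. It rests on 80 evaluable per arm, normal change scores, no difference between arms and a shared change of 0.1 to 0.5 SD that has no source in the documents. It is not an estimate of how often this trial would mislead. The matter concerns a specific objective, not the comparative main objective, and is worth correcting because the correction is nearly free.

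**What to change.** - **5.2.3:** restate as the comparison, between PRO-087 and each comparator, of the change from baseline to day 90 in goblet-cell density and in the other cytology measures the trial already records. Do not introduce a histological grade: 10.4 defines no grading scale.
- **Section 15:** state that conclusions about the effect of PRO-087 on cytology rest on the between-arm difference in change with its 95% CI; that the between-group ANOVA applies to quantitative variables; and that within-arm before/after results are descriptive (mean change with 95% CI).
- **14.1 and 14.1.2:** make the goblet-cell effectiveness statement consistent with this, so that a claim of effect does not rest on the PRO-087 arm alone.

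The cost is wording only, with no new patients, visits or samples. The sponsor gives up citing a within-arm improvement as evidence of effect, and the deciding interval is wider, by a factor of about 1.4 under the assumptions above.

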## 6. Summary

---

Drug product ID	PRO-087
Study drug:	0.1% sodium hyaluronate, free-preservative 0.18% chondroitin sulphate
Therapeutic indication:	Ocular surface lubricant
Protocol ID:	SOPH087-0415/IV
Sponsor:	Laboratorios Sophia, S.A. de C.V.
Version:	2
Date:	February 2016
Study title	Efficacy and Safety of the Ophthalmic Solution PRO-087 versus Systane ® Ultra and Systane ® Ultra Preservative Free on the Tear Film Dysfunction Syndrome from Mild to Moderate  Clinical trial

Main objective	To evaluate the effectiveness of preservative-free ophthalmic formulation PRO-087 (by Laboratorios Sophia, S.A. de C.V.) to restore the anatomical and physiological characteristics of the ocular surface, as well as its distribution and the characteristics of the mild to moderate tear film dysfunction syndrome compared to Systane ® Ultra and Ultra Systane ® preservative free (by Laboratorios Alcon, S.A. de C.V.).
Study design	Controlled, randomized, double-blind, masked clinical study, comparing the safety and efficacy of preservative-free PRO-087 vs Systane Ultra with preservative and Systane Ultra preservative free, in subjects with mild to moderate tear film dysfunction syndrome, for a period of 90 days plus 15 days of remote surveillance, in which one of the three agents will be administered (PRO-087, Systane® Ultra or Systane® Ultra preservative free) with a q.i.d. dosage. in both eyes, with regular follow-up visits (5 overall).
Variables to evaluate	
Best-corrected visual acuity
 
Intraocular pressure
 
Ocular surface
 
Anterior segment examination
 
Posterior segment examination
 
Tear film break-up time
 
Schirmer test
 
Corneal depithelization
 
Goblet cells count
 
Adverse events

Groups	Subjects with a clinical diagnosis of mild to moderate tear film dysfunction syndrome between 18 and 90 years old, without concomitant eye diseases nor requiring different treatments of any of the three interventions in this study They will be randomized in 3 groups where PRO-087, Systane® Ultra o Systane® Ultra preservative free will be administered.

## 7. STUDY DESIGN

---

### 7.1 *Design*

Controlled, double-blind, randomized, clinical trial comparing the safety and efficacy parameters between a group of subjects with a diagnose of mild to moderate tear film dysfunction syndrome under a regimen of ophthalmic solution lubricant drops PRO-087 versus subject under Systane® Ultra or Systane® Ultra preservative free, with the same diagnosis, with a follow-up of 90 days.

### 7.2 *Sample:*

288 patients with tear film dysfunction, classified as mild to moderate, will be included and randomized into 3 groups; the first being treated with PRO-087 ophthalmic solution, the second with Systane® Ultra ophthalmic solution, and the third with ophthalmic solution Systane® Ultra preservative free.

### 7.3 *Blinding:*

The double-blind study is a procedure in which the patient and the treating doctor ignore to which intervention group the study patient was assigned. To achieve the blinding of both the drug in research and both comparator drugs, these will be labeled in the same way (masking). Besides the figure of an unblinded pharmacist, who is responsible for the delivery of the medication to the patient, will be added. Blinding codes are protected by an outsider appointed by the study sponsor. The codes are also available in the research center (fully sealed), so that they can be consulted by the investigator in case a subject presents a serious adverse event, prior authorization from the study sponsor; the blinding also continues rigorous during the data analysis and interpretation.

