#### 7.4 *Pharmacological Intervention*

The pharmacological intervention will be the instillation of the ophthalmic solution in the bottom of the conjunctival sac during the waking period, in any of the following study groups:

1. Preservative free PRO-087 ophthalmic solution. Dropper bottle. Multidose  
1 drop every 4 hours for 90 days.
2. Systane® Ultra ophthalmic solution. Dropper bottle. Multidose.  
1 drop every 4 hours for 90 days.
3. Systane ® Ultra preservative free ophthalmic solution. Single-use vials.  
1 drop every 4 hours for 90 days.

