8.2 Drug Product of Study

The formulation PRO-087 is made of the following active agents: 1.80 mg/ml of chondroitin sulphate and 1.00 mg/ml of sodium hyaluronate, as well as the inactive agents: boric acid, decahydrate sodium borate, polysorbate 80, sorbitol, sodium chloride, dihydrate disodic edate, potassium chloride, hexahydrate magnesium chloride, purified water.

It is dispensed in a dropper bottle (which has a container closure system that allows to preserve the solution) for a multidose administration, as a preservative free ophthalmic solution of 10ml.

**Systane® Ultra** is made of the following active agents: 0.4% of polyethylene glycol 400 and 0.3% of propylene glycol, and the inactive agents: aminomethyl propanol, boric acid, hydroxypropyl guar, 0.001% of POLYQUAD® (polyquaternium-1) with conservative, potassium chloride, purified water, sodium chloride, sorbitol, hydrochloric acid/sodium hydroxide to adjust pH. It is dispensed in a dropper bottle for multidose administration, as ophthalmic solution of 10 ml.

**Systane® Ultra preservative free** is made of the following active agents: 0.4% of polyethylene glycol 400 and 0.3% of propylene glycol, and the inactive agents: aminomethyl propanol, boric acid, hydroxypropyl guar, potassium chloride, purified water, sodium chloride, sorbitol, hydrochloric acid/sodium hydroxide to adjust pH. It is dispensed as ophthalmic solution in single-use vials of 0.4 ml. Pharmacological intervention dosage with drug products of study: 1 drop 4 times daily for 90 days.

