### *8.3 Handling of the Drug Product of Study*

The drugs will be shipped from the storage center (located in Laboratorios Sophia S.A. de C.V.) previously weighed and packaged.

**The handling of the drug product of study will be the responsibility of the principal investigator in charge of the research center, including:**

- Receipt and storage of drug product of study. The receipt of the drug product of study must be acknowledged by signing and sending back the corresponding format. The drug product of study should be stored in a secure area with restricted access. Some special storage conditions are requested, such as to keep at room temperature of no more than 30° Celsius, for which the doctor will be provided, on loan during the study, with a thermos-hygrometer that records humidity and temperature. Principal investigator or pharmacist assigned must conduct a thermo-hygrometer reading at least once a day, keeping a record of:
  - Current temperature
  - Minimum temperature
  - Maximum temperature
  - Relative humidity
- Data review registered in the of thermo-hygrometer diary will be performed on the clinical monitor during monitoring visits and, in turn, the previously assigned responsible will perform a reading a day directly from the recorder screen, which will have to write down on the corresponding format.
- Expiration date will appear on each box and label.
- The investigator and/or pharmacist of the research center shall use the treatment delivered only for participating subjects of study.
- Drug product of study count:

The investigator and/or pharmacist of the Research Center and/or a person designated by the study team must fill in real time all the documents that the sponsor provides for the management of the drug product of study.

The study monitor will periodically check the handling and counting of the drug product of study.

At the end of the study, the principal investigator and the study monitor will complete a final inventory of drugs, and will record in the appropriate form.

The study monitor will collect the remaining drug product of study for storage and subsequent destruction, after quantifying the remaining amount in each container.

They must report all faults or damages of the drug product of study or of its packaging to monitor the study. The principal investigator shall notify the monitor all complaints received from a subject.

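### Identical labels cannot make a vial look like a bottle: subject masking is not secured for PRO-087 versus preservative-free Systane Ultra, and the 80% adherence rule has no stated base and no method for vials

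*Combined protocol and SAP*

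**What the plan says.** **Masking.** Section 7.3 defines the blind as one in which "the patient and the treating doctor ignore to which intervention group the study patient was assigned". For the products themselves it gives one measure: "these will be labeled in the same way (masking". It adds sealed codes and "an unblinded pharmacist, who is responsible for the delivery of the medication to the patient".

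**Containers.** Section 7.4 puts PRO-087 (arm 1) and Systane Ultra (arm 2) in multidose dropper bottles. Arm 3 is listed as "preservative free ophthalmic solution. Single-use vials", and section 8.2 confirms: "It is dispensed as ophthalmic solution in single-use vials of 0.4 ml". The labelling text in section 8.1 speaks of dropper bottles only.

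**Handling.** Section 8.3 states: "The handling of the drug product of study will be the responsibility of the principal investigator in charge of the research center". It allows the investigator and/or the pharmacist to keep the records, but at study end "the principal investigator and the study monitor will complete a final inventory of drugs". The final-visit list (day 90) puts the request to return product among the ophthalmic examination items. Section 17.6 has the containers sent back by the investigator.

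**Adherence.** Section 8.3 says the drugs are shipped "previously weighed and packaged" and that the remainder in each container is quantified before destruction. Section 17.6 weighs returned dropper bottles against their initial weight and accepts values above 80%. Lower values go to an intention-to-treat analysis, with a reference to the statistical section. Section 14 makes 80% adherence a condition of the efficacy, tolerability and safety rules.

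**The concern.** A subject instils the product for 90 days and sees the container every time. A shared label does not hide whether it is a bottle or a vial, so the container sets arm 3 apart from arms 1 and 2. The main objective names two comparators, and this affects the comparison with one of them.

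What is exposed depends on who makes the measurement. OSDI is completed by the subject (OSDI questionnaire in the appendices) and is an efficacy variable in section 14.1. Burning and foreign body sensation are reported by the subject and are tolerability variables in section 14.2. Break-up time, staining and hyperemia are graded by the examiner, so they are exposed only if the examiner learns the container. The Schirmer reading in millimetres and the goblet-cell count made at a single pathology center are less exposed.

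The container difference also reaches the adherence rule. A rule that weighs bottles has no procedure for vials, and a percentage without a denominator cannot be computed the same way by two people, even for bottles.

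**Working it through.** **1. Masking: the texts side by side**
- Claim: patient and treating doctor blind (7.3).
- Product-level measure: same label (7.3).
- Containers: bottle, bottle, vial (7.4, 8.2).
- Pharmacist and sealed codes protect delivery and the allocation list. They do not hide the container from the person who uses it.
- Result: the container separates arm 3 from arms 1 and 2. It does not separate arm 1 from arm 2.
- Size: 288/3 = 96 subjects in arm 3, and one of the two PRO-087 comparisons.

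**2. The 80%: can it be reproduced?**
No. Section 17.6 names the initial container weight as the reference for the difference, but not as the denominator of the percentage. Three bases are possible.

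Inputs from the plan: four doses a day, both eyes (section 6); 90 days; 0.4 ml vials and 10 ml bottles (8.2). Assumptions, because the plan gives no figure: drop volume 0.03 to 0.05 ml; empty bottle 2 to 8 g; 10 ml taken as 10 g; vials not carried over between doses; residues returned. Four doses a day is used for illustration only.

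Full use: 4 × 90 = 360 doses; 360 × 2 eyes = 720 drops.

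*(a) Share of initial gross weight.* A completely emptied bottle shows 10/(10+2) = 83% down to 10/(10+8) = 56%. Whether it passes depends on the weight of the plastic.

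*(b) Share of content.* For vials:
- One vial per dose: 2 × 0.03 = 0.06 ml and 2 × 0.05 = 0.10 ml; divided by 0.4 ml this is 15% and 25%.
- Two vials per dose: half of that, 7.5% and 12.5%.
- To exceed 80%, more than 0.8 × 0.4 = 0.32 ml must leave the vial: 0.32/0.05 = 6.4, so 7 drops; 0.32/0.03 = 10.7, so 11 drops. A dose for both eyes is 2 drops.

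A fully adherent arm-3 subject could not pass on this base.

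*(c) Share of expected use.* 720 × 0.03 = 21.6 ml; 720 × 0.05 = 36 ml. The 80% line is then 17.3 ml or 28.8 ml. A subject who dispensed 21.6 ml scores 100% at 0.03 ml per drop and 21.6/36 = 60% at 0.05 ml. This base is workable for bottles once a drop volume is stated. For vials it needs a count, which 17.6 does not provide.

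**3. Where the rule leads**
- Cut-off wording: 80% (14.1), at least 80% (14.2 and the safety rule), above 80% (17.6). A subject at exactly 80% is classified differently in different sections.
- Consequence: 17.6 refers to section 15. Section 15 has no adherence rule and uses the intention-to-treat label for subjects who do not complete the visits.

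**The case against.** **The subject may not know what a vial means.** Seeing a vial is not the same as knowing the product. What subjects are told would stand in the consent pages, which are not available here. This stands: a reader might infer that arm-3 subjects are certainly unmasked, and the documents do not show that. They show only that nothing in the plan prevents it.

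**The exposure is partial.** A PRO-087 subject holding a bottle cannot tell it from arm 2 by container type. Section 13.3 sizes the trial on Schirmer, which is less exposed. Both points stand and limit the concern to subject-reported outcomes in one comparison.

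**The examiner is protected.** A reader might infer from section 8.3 and the visit lists that the principal investigator handles the product and is unmasked. The documents do not support this. Section 7.3 gives delivery to an unblinded pharmacist, section 8.3 repeatedly allows investigator and/or pharmacist, and responsibility for handling can mean site accountability. The visit lists are checklists: the final-visit examination list also contains the scheduling of a phone call. What remains is a lack of alignment. The final inventory, the return request and the return of containers are not reserved for the pharmacist.

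**Adherence is already reviewed in all arms.** The schedule in section 9 has a journal review at every visit. That is true and useful, but section 17.6 does not base the 80% on it.

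**The figures rest on assumptions.** No passage says that opened vials come back with their residue. The 100% versus 60% contrast reflects an unstated drop volume that could be measured. It should not be read as a 40-point error in adherence.

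**Conclusion.** The point holds in two parts and should be corrected; it does not invalidate the trial.

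First, subject masking is claimed but not secured for PRO-087 versus preservative-free Systane Ultra. In that comparison OSDI and reported symptoms are open to expectation bias to the extent that subjects know or guess the product. The size of that bias cannot be estimated from the documents. The wider conclusion, that the double blind fails throughout or for the examiner, is not supported.

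Second, the 80% adherence condition in section 14 cannot be applied to arm 3 as written, nor on the same basis in all arms. On a content base a fully adherent arm-3 subject would show about 15 to 25% at one vial per dose, or half that at two, given 0.03 to 0.05 ml drops and returned residues. The absence of a base and of a vial procedure is plain from section 17.6 and depends on none of these assumptions. Section 15 also lacks the rule for results below 80% to which 17.6 refers.

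**What to change.** 1. **Sections 7.3, 8.3, 11 and 17.6.** Have only the unblinded pharmacist dispense, receive, count and inventory product, in closed opaque boxes. Take delivery and return off the examiner's visit lists. Tell subjects not to show or describe the container to the examiner. Extend section 8.1 to the vials.
2. **Sections 7.1 and 7.3.** State that with these steps the comparison with arm 3 is assessor-masked and that subject masking is not assured. Interpret OSDI and reported symptoms in that comparison accordingly.
3. **Section 17.6.** Define the 80% as a share of expected use and apply it in all arms from the subject journal already reviewed at each visit. Keep bottle weights, with a stated drop weight per product, and, if feasible, unused-vial counts as supporting data: weights measure volume dispensed, whereas counts measure vials opened.
4. **Sections 14 and 15.** Use one cut-off wording in 14 and 17.6, and state in 15 how results below 80% are analysed.
5. **Before expected use is set.** Reconcile the dosing statements (sections 6 and 8.2 versus 7.4, which says every 4 hours while awake and may or may not mean the same), the number of vials per dose, and the bottle content (5 ml on the sample label in 8.1.1 versus 10 ml in 8.2).

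**Cost.** Protocol wording and boxes. The boxes help the examiner's masking but do not restore the subject's, so the double-blind claim becomes weaker for one comparison. Journal adherence is self-reported. Vial counting is heavy, which is why it is only supporting: 96 × 360 = 34,560 vials at one per dose and 96 × 720 = 69,120 at two. These are upper figures, because 96 per arm includes the allowance for losses. Counting only unused vials gives at most 20% of this, 6,912 to 13,824, if every subject used at least 80% and exactly the expected number was dispensed. Discarded vials would then count as used.
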